8.3.2 Exclusion Criteria

1. Recipients that have participated in the CLTD5446 study.

8.3.3 Criteria and procedures for subject's withdrawal or discontinuation

Subjects can decide to withdraw from the investigation without indicating any reasons at any stage. Recipient's datasets will then be excluded from the CI532 retrospective evaluation.

8.3.4 Point of enrolment

Subjects are enrolled into the clinical investigation when they have signed the Informed Consent Form.

8.3.5 Total expected duration of the clinical investigation

It is expected to retrospectively collect CI532 hearing performance data between March 2017 to November 2018.

8.3.6 Expected duration of each subject's participation

Not applicable due to the retrospective data collection.

8.3.7 Number of subjects required to be included in the clinical investigation

The anticipated number of datasets is ≥ 150 .

8.3.8 Estimated time needed to select this number (i.e. enrolment period)

The estimated time to collect ≥ 150 datasets are 21 months.

8.4 Procedures

No product or procedure related training is required since we will collect pseudo-anonymised clinical follow-up data hearing performance data and device characteristic data exported from clinical software provided with this CE marked product. The clinics will be trained by the Clinical Project Manager how to pseudo-anonymise the clinical data.

The clinic will recruit patients by phone and or mail. Based on their clinical database they select patients that fulfil the inclusion criteria and will provide the Patient Informed Consent to these patients by mail. Potentially a follow-up call will be conducted by the clinic to answer open

questions from the recipient. After patients have signed the Patient Informed Consent they will send it back to the clinic.

After the clinic has received the signed Informed Consent the clinician enters the available hearing performance data from the recipient's hospital file into the electronic data capturing system in a pseudo-anonymized way (See section 15.2).

The device/patient characteristics will be collected through anonymized computer record files ("cdx") produced by the CustomSound software which is routinely used to fit the CI532 recipients. The cdx files will be pseudo-anonymized with a unique patient code and sent to Cochlear.

Study subjects did follow clinical routine treatment practices and this retrospective approach does not impact routine clinical treatment at the implanting centre.

The surgeon's questionnaire will be filled by at least one surgeon per site once that surgeon has achieved a minimum experience of ten (10) CI532 surgeries. This could be in the beginning or close to the end of the study based on the surgeon's experience with CI532. Completed paper surgeon's questionnaire will be shipped to the clinical project manager by regular mail for further handling and analysis.

8.5 Monitoring Plan

Please refer to the Monitoring Plan.

9 Statistical Considerations

Please refer to the Statistical Plan.

Depending on the clinic different types of speech understanding measurements in noise will be measured. For example the OLSA is an adaptive test in which the 50% point of the discrimination function is measured. This point of the discrimination function has the maximal steepness and is most sensitive to changes in hearing function. On the other hand, HSM is a test with a fixed SNR. In this test different points along the discrimination function are being measured. The steepness changes at these different points of the discrimination function. Therefore, there is no linear relation between the test results for the OLSA and HSM sentence materials and it is not possible to calculate a linear relation like "a change of x dB SNR in OLSA corresponds to y% change in HSM". Therefore the type of speech test material in noise has to be considered as dependent variables for analysis of group performance.

10 Data Management

Data collection is performed through [REDACTED], a web-based system for electronic data capturing. Site personnel will be trained to use this system. Data validity has to be confirmed by the investigator through an electronic signature. An audit trail is kept by this system and data clarifications may be generated by the system and sponsor personnel after review of data.

[REDACTED] is a system that has been verified and validated by the vendor. Installation of the system within Cochlear has been validated as well. Study-specific implementations are validated by Data Management and consist of verification that all required items are included, validity of edit checks and appropriate functionality of conditional fields. The study-specific data in [REDACTED] can only be accessed by those that have been allocated their individual account, which are personnel of the investigational sites, Clinical Project Manager, Study Monitors and Data Management staff.

11 Amendments to the RSP

No changes in the study protocol shall be effected without mutual agreement of the investigator(s) and the Sponsor. All changes must be documented by signed RSP amendment. Substantial changes will require notification to the Ethics Committee.

12 Deviations from the RSP

The expected number of deviations is anticipated to be low due to the retrospective nature of the study. Only datasets of CI532 recipients that have signed the Patient Informed Consent will be part of this evaluation. Any deviations by the clinical investigator shall be documented and reported to the Sponsor and the EC as necessary.

13 Device accountability

Not applicable because of the retrospective approach in already implanted CI532 recipients.

14 Statements of compliance

14.1 Declaration of Helsinki and compliance with standards

The clinical investigation shall be conducted in accordance with the ethical principles that have their origin in the Declaration of Helsinki (2013), the EN ISO 14155:2011 and any regional or national regulations, as appropriate. This retrospective investigation will be registered on ClinicalTrials.gov.

14.2 Ethics Committee Approval

The clinical investigation shall not commence prior to the written favourable opinion or approval from the EC is obtained.

The investigator shall submit the final version of the clinical investigation plan, the informed consent and all subsequently required documents to the Ethics Committee. A copy of the Ethics Committee opinion/approval shall be provided to the sponsor.

Sponsor and investigator shall continue the communication with the EC as required by national regulations, the clinical investigational plan or the responsible EC.

Any additional requirements imposed by the EC shall be followed.

The investigator shall submit the appropriate documentation if any extension or renewal of the EC approval is required. In particular substantial amendments to the clinical investigation plan, the informed consent, or other written information provided to subjects must be approved in writing by the EC.

The investigator shall send written status summaries of the investigation to the EC regularly as per local EC requirements.

Upon completion of the clinical investigation, the investigator shall provide the EC with a brief report of the outcome of the clinical investigation as per local EC requirement.

The clinical investigation is covered by the Cochlear global cover insurance. No additional clinical trial insurance is required, because no exposure to recipients applies.

14.3 Audits and Supervision

Study sites and study documentation may be subject to Quality Assurance audits during the course of the clinical investigation. In addition, regulatory bodies at their discretion may conduct inspections, during and after study completion.

14.4 Study Records

The investigational site will receive and has to maintain an Investigator's File which does include without limitation at a minimum the signed Retrospective Study Plan, the EC approval letter, completed Informed Consent Forms, Investigator copies of all CRFs, correspondence with the Sponsor and third parties related to the study, a subject identification list, and a site delegation and signature sheet. All study records and source documents shall be archived at the investigational site, which aims to be the implanting centre for this study, for at least 15 years after the end of the study.

15 Informed consent process

15.1 Obtaining informed consent

The investigator must obtain written informed consent from the subject prior to any clinical investigation related activity, and after explaining the rationale for and the details, aims and objectives of the study and the extent of the subject's involvement. Ample time must be provided for the subject to inquire about details of the investigation and to decide whether to participate. All questions about the investigation should be answered to the satisfaction of the subject or the subject's legally acceptable representative. Subjects must not be coerced or unduly influenced to participate or to continue to participate in an investigation.

Each subject and the person who conducted the informed consent discussion must sign and date the informed consent form. Where required, a witness must sign and personally date the consent form.

A copy of the information leaflet and consent form must be given to the subject. All signed Informed Consent Forms must be archived in the Investigator's File at the investigational site, according to the requirements of the country's health regulations, but for a minimum of 15 years after completion of the clinical investigation.

The investigator shall forward any amendment made to the approved subject informed consent for review to the Sponsor or Study Monitor and any other written information to be provided to the subject, prior to submission to his EC.

15.2 Data Privacy

Subjects will be identified on CRFs or similar documents by a unique subject identification code. No personal identification of private information will be extracted. Completed CRFs or similar documents are confidential documents and will only be available to the Sponsor and their representatives, the investigator, the investigational statistician, and if requested to the Ethics Committee and national regulatory authorities.

The investigator and site staff will not include the name of any subject in any CRF or other forms, electronic files, publication, or submission to a regulatory authority; will not otherwise disclose the identity of any subject; and, in any CRF, will refer to each subject by his/her unique identification code.

An identification code (pseudo-anonym) will be used [REDACTED]

[REDACTED]

[REDACTED]	[REDACTED]
[REDACTED]	[REDACTED]
[REDACTED]	[REDACTED]

16 Incident reporting

16.1 Incident Reporting

This investigation is performed using CE marked devices thus requiring reporting of incidents under the MEDDEV 2.12-1 via Cochlear's policy & procedures for complaints- and issues handling as implemented routinely for all products under postmarket surveillance as part of our mandated postmarket vigilance. Due to the retrospective approach, any incidents may have already been reported as part of the hospital's routine via Cochlear's policy & procedures for complaint and issue handling. To close any potential gaps, we will actively ask if all complaints and incidents have been reported to Cochlear via Cochlear's policy & procedures for complaint and issues handling in the CRFs.

16.2 Definition of Incident

"Any malfunction or deterioration in the characteristics and/or performance of a device, as well as any inadequacy in the labelling or the instructions for use which, directly or indirectly, might lead to or might have led to the death of a subject, or user or of other persons or to a serious deterioration in their state of health."

16.3 Reporting process

As is routine, the investigator shall report all incidents without undue delay to the sponsor, EC and as applicable to the NCA:

Name of contact person of the sponsor: [REDACTED]

Fax: [REDACTED]

E-mail: [REDACTED]

The Sponsor shall assess all reported incidents with the investigator, co-ordinate appropriate actions, if required, and provide the NCA with a final report.

The investigator shall report all incidents to his/her EC using the applicable report form as per national requirement.

17 Suspension or premature termination

The Sponsor will withdraw from sponsorship of the clinical investigation if,

- 1.) major non-adherence to the RSP is occurring
- 2.) it is anticipated that the subject recruitment via patient informed consent signature will not be adequate to meet the objectives of the retrospective investigation

18 Publication Policy

Investigators will be able to publish and/or present their own data. The publishing investigator will provide the sponsor with a manuscript copy of the abstract and paper at least 30 days in advance of publication or presentation. If the publication contains information that the sponsor at his discretion finds worth protecting in the form of a patent or trademark etc., the sponsor has the right to delay the publication or presentation for 90 days.

After finishing the study it is planned to generate a joint publication by the clinical investigator(s) and the sponsor. The responsibility for writing the publication is with the Coordinating Investigator. In case of multi-centre investigation, the authorship will be based on contribution of complete datasets and contribution to paper preparation according to the rules of the journal chosen for publication. The joint publication must be reviewed by the sponsor at least 30 days in advance to any release of publication. If the publication contains information that the sponsor at his discretion finds worth protecting in the form of a patent or trademark etc., the sponsor has the right to delay the publication or presentation for 90 days.

19 Bibliography

Holden et al. (2013): Factors affecting open-set word recognition in adults with cochlear implants. *Ear Hear.* 34(3):342-60

CI532 Clinical Evaluation Report, version: 4, date: 15.06.2015, pages 46-49

CLTD5446 CIP version: 4, date: 18.06.2015

1 INTRODUCTION

This is the statistical analysis plan for a Multi-center retrospective data collection of already available routine clinical data to assess hearing performance outcome in a cohort of CI532 recipients.

The primary objective is to collect available speech perception data obtained in quiet and in noise for the pre-operative daily listening condition and at 3 and 6 months post CI532 implantation best aided conditions.

1.1 Objectives

1.1.1 Primary Objective

To assess available speech understanding in quiet and in noise pre-operative (daily listening condition) and at 6 months post CI532 implantation (best aided conditions).

1.1.2 Secondary Objective

1. To compare available aided (daily listening condition) and unaided pure tone audiometric thresholds obtained before surgery and at 6 months after CI532 surgery
2. To get insight for available CI532 device characteristics (electrode impedances, NRT, MAP T and C levels) and patient characteristics (datalogging) (cdx files)
3. To assess subjective surgeon's opinion and clinical experience with CI532 via a questionnaire

1.2 Endpoints

1.2.1 Primary Endpoint

1. Change from pre-op (daily listening condition) baseline speech understanding in quiet and in noise at 6 months post-op (best aided conditions).
2. The proportion of the recipient cohort in percent examined showing post-operative improvement per test and listening condition.

1.2.2 Secondary Endpoint

1. Change from pre-op baseline aided (daily listening condition) and unaided thresholds at 6 months post-operative
2. Defined normative CI532 device characteristics (electrode impedances, NRT, MAP T and C levels) and patient characteristics (datalogging)
3. Combined subjective clinical experience and opinion about CI532 from surgeons

1.3 Hypotheses

1.3.1 Primary hypotheses of retrospective study

1. H_0 : Speech understanding in quiet and in noise at the 6 months post-operative visit are equal with speech understanding in quiet and noise at the pre-operative evaluation visit
 H_1 : Speech understanding in quiet and in noise at the 6 months post-operative visit is better than speech understanding in quiet and noise at the pre-operative evaluation visit
2. H_0 : The proportion of the recipient's cohort examined showing post-operative improvement per test and listening condition is below 80% for the 6 months post-operative visit.
 H_1 : The proportion of the recipient's cohort examined showing post-operative improvement per test and listening condition is $\geq 80\%$ (Dowell, Hollow & Winton, 2004) for the 6 months post-operative visit.

2 STATISTICS

A total of $n=150$ patients will be assessed. It is expected to enrol approximately 30 subjects per site to compensate the variability of speech understanding tests in noise across sites with a decent power per site.

At different points during follow-up data exports and interim analyses will be conducted. The first data export with available datasets is expected to take place in August 2016. Over the study period it is expected to gradually increase the number of available datasets and therefore also the number of datasets for following interim analyses. The final analysis is expected to cover 150 datasets by the end of July _____

The interim analysis will be of descriptive nature only to maintain the nominal type I error of 5%. Formal hypothesis testing will be confined to the final analysis.

The level of significance for all statistical tests is $\alpha=5\%$, 2-sided.

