8.1 General

The aim of this study is to assess hearing performance based on clinically available routine hearing measures to demonstrate changes from pre- to post-CI treatment for patients implanted with the CI532 cochlear implant in a German speaking cohort.

The study is multi-centric including five centres in Germany (Kiel, Erlangen, Frankfurt am Main, Freiburg, Hannover) to retrospectively gather bench mark hearing performance data of CI532 recipients. The centres have been chosen due to their experience with CI532 and the availability of hearing performance data with CI532.

The hearing performance data located in patient's hospital file will be pseudo-anonymized by the clinician and entered into the study database. Therefore no bias is expected and no corrective action on a potential bias is required.

The hearing performance data has been gathered as part of the routine clinical measurements pre-operatively and at 3 and 6 months post-operatively for speech understanding in quiet and in noise and for unaided and aided thresholds. In addition medical history, anomalies in terms of electrode placement and recipient's device characteristics will be collected. Surgeons with CI532 experience will be asked to retrospectively evaluate the handling and usability of CI532 during conducted surgeries.

A first data export will be conducted after 50 datasets have been entered to informally view the datasets per centre. Over the study period clinicians are asked to gradually enrol the CI532 recipient's based on available datasets. It is expected to enrol ≥ 150 datasets until end of the study.

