8.2 Datasets for the commercially available CI532

The pre-operative datasets are dependent on the recipient's daily device use. This is dependent on the advice of the recipient's ENT practitioner or clinical routine and could consist of either: a) an unaided condition, b) hearing aid unilateral/bilateral, or c) unilateral CI. Preoperative device use and hearing performance will be collected and considered for analysis as the comparator to the postoperative hearing performance.

The post-operative best aided conditions are dependent on the clinical routine advice and could consist of: a) a contralateral hearing aid, b) unaided contralateral ear, or c) contralateral

CI. Evaluation of electrode placement and location in the scala, by e.g. imaging data, will be considered during postoperative hearing performance analysis.

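### The 92.8% power for primary hypothesis 2 assumes 150 paired scores on one test; it does not carry over to a noise test used only at some clinics, and the SAP gives no expected n or hypothesis 2 power for any noise test.

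*SAP*

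**What the plan says.** **Unit of hypothesis 2.** In SAP 1.3.1 the null hypothesis is that the share of recipients "showing post-operative improvement per test and listening condition is below 80% for the 6 months post-operative visit". The protocol's hypotheses (7.3.1) say the same.

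**Noise tests.** Protocol section 9: "Depending on the clinic different types of speech understanding measurements in noise will be measured". It gives OLSA (adaptive, dB SNR) and HSM (fixed SNR) as examples, says that "there is no linear relation between the test results for the OLSA and HSM sentence materials", and concludes that "the type of speech test material in noise has to be considered as dependent variables for analysis of group performance".

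**Numbers.** Protocol 8.1: "The study is multi-centric including five centres in Germany". SAP section 2 sets the total at 150 and expects "approximately 30 subjects per site to compensate the variability of speech understanding tests in noise across sites with a decent power per site". Protocol 8.3.7 gives 150 as a minimum.

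**Power for hypothesis 2.** SAP 2.1 turns it into a one-sample exact binomial test against 0.80. Table 3 covers n=100, 125 and 150 at true rates 0.875, 0.90 and 0.925. The text quotes 92.8% for 0.90 at n=150. No row is linked to a named test.

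**Power for hypothesis 1.** SAP 2.1 names the Freiburg monosyllables for the 20% difference, and 1.4 dB (OLSA) and 30% (HSM) for noise. Table 1 is a paired t-test with mean difference 1.0 and SD 3.0, the SD resting on an earlier OLSA study. Table 2 uses 0.5 against 0.7. No table uses the HSM 30%.

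**The concern.** A power figure belongs to a test with a given number of evaluable pairs. If hypothesis 2 is judged separately for each speech test, n for a noise test is the number of patients whose clinic used that test at both visits, not the study total. The SAP states a single power at the study total and never says how many patients are expected on each noise test.

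Hypothesis 2 is primary. In a smaller group the observed rate needed to reject is higher, so a noise test could miss the 80% criterion because few clinics use it rather than because few patients improve. A reader who has only the 92.8% would not expect that. The remark about power at each site suggests that the issue was noticed, but no figure supports it and no hypothesis is named.

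**Working it through.** **Inputs.** P0 = 0.80; P1 = 0.875, 0.90, 0.925; two-sided 5%; N = 150; five sites of about 30 (SAP 2 and 2.1, Protocol 8.1). For OLSA: difference 1.0 (Table 1) or 1.4 dB (SAP 2.1 text); SD 3.0 (Table 1) or 2.29 (the source-trial value in SAP 2.1).

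**Step 1: reproduce Table 3.** Let r be the smallest count with P(X ≥ r | n, 0.80) ≤ 0.025. Power is P(X ≥ r | n, P1); the lower tail adds nothing visible at these rates. At n=150, r=130 (upper tail 0.0224), and power is 0.6761 / 0.9279 / 0.9958 at the three rates. At P1=0.90, n=125 (r=109) gives 0.8811 and n=100 (r=89) gives 0.7030. All agree with the SAP.

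**Step 2: the same rule at smaller n.** The number of sites per noise test is not in the documents. The site rows below assume 30 paired scores per site.

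| Paired n | Reject at | Observed rate needed | Power at 0.875 | Power at 0.90 | Power at 0.925 |
|---|---|---|---|---|---|
| 150 (5 sites) | 130 | 86.7% | 67.6% | 92.8% | 99.6% |
| 120 (4 sites) | 105 | 87.5% | 56.8% | 85.6% | 98.2% |
| 90 (3 sites) | 80 | 88.9% | 42.1% | 71.3% | 92.6% |
| 75 (half of 150) | 67 | 89.3% | 39.6% | 66.6% | 89.2% |
| 60 (2 sites) | 55 | 91.7% | 22.3% | 43.7% | 70.6% |
| 30 (1 site) | 29 | 96.7% | 9.6% | 18.4% | 33.1% |

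The last row can be checked by hand at 0.90: 30 × 0.9^29 × 0.1 + 0.9^30 = 0.1413 + 0.0424 = 0.1837.

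**Step 3: two noise tests sharing 150 patients.** Assumption: two tests, one per patient. The smaller group then has at most 150/2 = 75. Over all n up to 75, power is highest at n=75: 66.6% at 0.90 and 89.2% at 0.925. At 0.90, 80% power is first reached at n=107, so both tests would need 2 × 107 = 214 patients, more than 150. At 0.925 it is first reached at n=62, and 2 × 62 = 124 fits within 150. At 0.925 both tests can therefore reach 80%, but only if the split is fairly even: at three sites against two, the smaller group of 60 has 70.6%.

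**Step 4: hypothesis 1 on OLSA.** Paired t-test, noncentral t with noncentrality (difference/SD) × √n. Difference 1.0 and SD 3.0 give 0.910 at n=100 and 0.982 at n=150, as in Table 1. At the SAP's 1.4 dB with SD 3.0, power is 99.2% at n=90, 97.9% at n=75, 94.5% at n=60 and 69.5% at n=30. With SD 2.29, n=30 gives 89.9%. A smaller OLSA group matters little here until it is down to one site.

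**The case against.** **Pooled reading.** SAP 2.1 speaks of a single one-sample test, section 5 defines a binary response as better than pre-op, and section 8.2 describes one binomial test and keeps centre-specific thresholds as a covariate in the modelling. One could read this as responders pooled over clinics, each on their own noise test, with n=150. It is a feasible analysis, but it is not the hypothesis as worded in both documents, and the covariate model only complements the formal test. The pooled reading does not rescue the figure for a per-test claim.

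**The quiet test.** Clinic-dependent testing is described only for noise, and SAP 2.1 names the Freiburg monosyllables. The 92.8% may well be right for that test if all 150 patients have both scores. This stands, and the point is confined to noise.

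**The split is unknown.** This also stands. The range at 0.90 runs from no loss (all 150 on one noise test) to 18.4% (one site). Protocol section 9 names OLSA only as an example beside HSM, some patients may have both, and enrolment may exceed 150. A reader might infer that the noise tests are shown to be underpowered. The documents do not support that; they show that the information needed to judge is missing.

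**No noise power at all?** A reader might also infer that the SAP has no power calculation for any noise test. That is wrong: Table 1 rests on OLSA data, for hypothesis 1. It does, however, place 100 to 150 patients on OLSA.

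**Per-site power.** For OLSA under hypothesis 1, 69.5% to 89.9% at n=30 gives the remark some basis. For hypothesis 2, 18.4% does not.

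**Weight.** This is a retrospective benchmark study, and the planned 95% confidence intervals would show the imprecision of a small group. That limits the harm but does not correct the stated power.

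**Conclusion.** The point holds for hypothesis 2 on noise tests and should be fixed. The calculation behind the 92.8% is correct; its scope is not stated. It applies to a test with 150 paired pre-op and 6-month scores and not to a noise test used at only some clinics. The SAP gives no expected n per noise test, no hypothesis 2 power at such an n, and no calculation with the HSM 30%.

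At a true rate of 0.90 and about 30 pairs per site, power falls from 92.8% to 85.6%, 71.3%, 43.7% or 18.4% for four, three, two or one sites. On the further assumption of two noise tests, one per patient, sharing 150 patients, the smaller group has at most 66.6%, so both cannot reach 80%. That conclusion is specific to 0.90, the rate the SAP chose for its quoted power; it does not hold at 0.925.

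If the listening condition in hypothesis 2 also separates the pre-operative device states, which "could consist of either: a) an unaided condition, b) hearing aid unilateral/bilateral, or c) unilateral CI", n falls further. No split is given, so I put no number on it.

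**What to change.** In SAP 2.1:

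- Limit the 92.8% statement to tests expected to have paired pre-op and 6-month scores in all 150 patients, and name them.
- For each noise test, list the sites that use it and the expected paired n. Add Table 3 rows at those n for 0.875, 0.90 and 0.925, and Table 1 rows at the OLSA n, including 1.4 dB.
- In SAP section 2, tie the per-site power remark to hypothesis 1 with its figure, or delete it.
- Optionally, add a supplementary pooled noise-responder analysis that applies the section 5 definition to each patient's own noise test. It needs no conversion between dB and percent. It should stand beside the per-test hypothesis, not replace it.

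Cost: one query to the five sites, which hold the records, plus revised text and tables. The stated powers for noise will look less favourable. No extra patients or measurements are needed. The change makes the power statement accurate; it does not enlarge a small group.
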